9.12 Clinical Assessments and Procedures

Calculations or measurements of specific parameters are required, as indicated in the schedule of assessments. Instructions for determining these parameters are provided in the following sections.

9.12.1 Height and Weight

Weight measurements will be performed with shoes removed and bladder empty. Participants will be weighed on the same scale at all visits.

At least two separate measurements will be taken at each visit. If the two measurements are more than 0.5 kg (1.1 lbs) apart, a third measurement will be taken. The two closest values will be selected and entered in the database.

Measurement of height will be performed with the participant's shoes removed. The participant's knees will be straightened, and head held upright.

9.12.2 Blood Pressure and Heart Rate

In-office, seated, resting blood pressure assessment:

The participant should be seated comfortably with their back supported and the upper arm bared without restrictive clothing. Feet should be flat on the floor and legs will not be crossed. The participant will rest in this position for at least five minutes prior to the first reading.

At screening:

Seated blood pressure will be checked in both arms and if different the arm with the higher systolic blood pressure reading will be taken for measurements. If the systolic blood pressure is the same in both arms, the arm with the higher diastolic blood pressure will be used. If both are equal, then the left arm will be used. In the chosen arm, a second measurement will be taken at least 1 minute from the first measurement. If a difference of more than 8 mmHg exists between the two readings a third reading will be taken. An average of the two lowest readings from the chosen arm will be taken for the determination of inclusion into the study. As per the QI's opinion, a high office blood pressure should be rechecked manually after the participant is given a glass of water and is seated for 15 min. Also, participant should be queried about their usual blood pressure.

The arm chosen for use at the initial visit will be documented in the study file and used in all subsequent visits.

At study visits:

Once enrolled in the study, BP will be measured in the chosen arm. Three readings will be made, averaged and recorded in the chart.

Heart Rate (beats/min) will be measured using the reading on the automated blood pressure monitor, or manually by the clinical coordinator placing their index finger on the participant's radial artery while observing a timer and counting the number of beats over 30 seconds and then multiplying the number by two. This is repeated for a total of three measurements.

9.12.3 Blood Sample Collection

Blood samples will be collected during visit 2, visit 5, visit 6, and visit 9 as per the procedures for outlined below.

Participants will be placed in a comfortably seated position with their arm fully extended and supported by a pillow. Aa tourniquet will be applied to the desired arm 3-4 inches above the elbow or 4-5 inches above the wrist to facilitate locating a vein. Once chosen, the site will be cleansed with 70% isopropyl alcohol, allowed to dry, and the IV catheter will be inserted piercing the skin and into the vein to the desired depth. With the catheter in place, the positive displacement connector will be attached to the blood collection hub, a patch will be placed over the entire system, and the access device will be connected to the positive displacement connector. The vacutainer tube will then be allowed to fill as per the Order of Draw and Fill Level Chart. When required, the filled tube will be disengaged, and another tube engaged. After disengaging, each tube will be inverted gently a number of times as per the Order of Draw and Fill Level Chart. This collection process will be repeated for the remaining blood collection time points until the number of blood draws had been satisfied. The IV catheter will be kept patent with a saline. To remove the IV catheter, the patch will be peeled back, and the tape will be peeled back to ensure the system is not removed from the connector. A cotton ball will be placed at the puncture site, and the system removed in a swift motion. Pressure will be applied to the site for a minimum of 30 seconds.

Once the clotting has occurred, a bandage/cotton ball and tape will be applied over the puncture site. Alternatively, if blood drawn via the catheter is unsuccessful, direct venipuncture will be conducted.

Samples will be collected as per the following procedures for venipuncture at visit 1, visit 3, visit 4, visit 7 and visit 8.

Participants will be placed in a comfortably seated position with their arm fully extended and supported by a pillow. All appropriate tubes, needle, alcohol and cotton balls will be retrieved. A tourniquet will be applied to the desired arm 3-4 inches above the elbow or 4-5 inches above the wrist and the participant will be requested to open and close their fist a few times to facilitate locating a vein. The vein will be gently pressed to determine its direction, approximate size and depth. The tourniquet will be removed, and the chosen site will be cleansed with 70% isopropyl alcohol and cotton ball or alcohol pad. The site will be allowed to dry, and the tourniquet will be reapplied, and the participant will be required to make a tight fist. The vacutainer system (needle placed in the holder) will be held and the vein will be anchored. The needle will be inserted into the skin and vein at 30_o angle. The vacutainer tube will then be allowed to fill as per the *Order of Draw* and *Fill Level Chart*. When required, the filled tube will be disengaged, and another tube engaged. After disengaging, each tube will be inverted gently a number of times as per the *Order of Draw* and *Fill Level Chart*. The tourniquet will be removed when the last collection tube is half full. A cotton ball will be placed over the site, and the needle will be removed in a swift motion. Pressure will be applied to the site for a minimum of 30 seconds. Once the clotting has occurred, a bandage/cotton ball and tape will be applied over the puncture site

9.12.4 Checklist Individual Strength Questionnaire (CIS) Questionnaire

The Checklist Individual Strength Questionnaire is a validated questionnaire for healthy working population (Appendix 15.5). This is a 20 items questionnaire scored on a 7-point scale measuring subjective fatigue experience, reduced concentration, reduced motivation and reduced physical activity level. The Questionnaire will be administered to participants on visit 2 to visit 8.

investigate the safety and efficacy of RiaGev[™] in healthy adults

9.12.5 Saliva Sample Collection

Participants will collect salivary cortisol samples using the Salivette collection device. Saliva sample will be collected within 15 minutes of waking and prior to eating on the mornings of all visits, except screening (Visit 1). To ensure proper collection, participants will be provided instruction by Prism clinical site.

9.12.6 Maximum Heart Rate Treadmill Test

Participants will complete a graded treadmill test following a ramped Bruce protocol (9,10) at their screening visit (Appendix 15.4). Participants will continue to advance stages until volitional exhaustion by the participant. Throughout the test, participants heart rate will be monitored and recorded with a chest strap heart rate monitor. Successful competition of the test will be achieving 85% or greater of age predicted maximum heart rate (220-age) (9).

9.12.7 Treadmill Exercise

Participants will determine their max heart rate (HR) in the clinic at visit 1 (screening, Day 0) via graded treadmill test with a chest strap heart rate monitor (Section 9.12.6). Eligible participants will return and exercise on the treadmill at visit 2 (period 1, Day 1), visit 5 (period 1, Day 8), visit 6 (period 2, Day 1), and visit 9 (period 2, Day 8). On the day of the exercise, participants will be instructed to warm up on the treadmill first for five minutes at a leisurely walking pace. When the participants are ready, speed will be increased to 60% of participant's HRmax with 5% grade incline and they will be instructed to walk on the treadmill for 30 minutes or until exhaustion (11).

9.12.8 Skin Fluorescence (Optional)

The AngioExpert device may be optionally employed to evaluate the 460 nm fluorescence of the skin in response to activation by the 340nm UV light. The wavelength of 340 nm emitted in the FMSF method is only specific to NADH, thus no other substance in the skin can be excited. The AngioExpert will be used to continuously measure the 460 nm fluorescence from the most superficial skin cells in the forearm at rest, then during controlled ischemia triggered by total occlusion of the brachial artery by the brachial blood pressure cuff, and, finally, during reperfusion after deflation of the blood pressure cuff (12).

9.12.9 Food Records

Participants will be asked to record their food consumption during the study. This data will be used to calculate and analyze their daily calories, macronutrient and micronutrient intake throughout the study using a software called Nutritics. The food records will be reviewed by trained staff at the visits and participants will be counseled with dietary suggestions as required. All participants will be provided with instructions on how to complete their food records.

9.13 Compliance

Compliance will be assessed by counting the returned unused study product at each visit. Compliance is calculated by determining the number of dosage units taken divided by the number of dosage units expected to have been taken multiplied by 100.

$$\frac{number\ of\ dosage\ units\ taken}{number\ of\ dosage\ units\ expected\ to\ have\ been\ taken}\times 100\%$$

In the event of discrepancy between the information in the treatment diary and the amount of study product returned, use will be based on the product returned unless an explanation for loss of product has been provided. Participants found to have a compliance of <80% or >120% will be counseled. A compliance of <70% or >130% will be considered as non-compliant and any participant demonstrating non-compliance for two consecutive visits will be withdrawn from the study.

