7.4 Early Withdrawal

Personal reasons:

As stated in the Informed Consent Form, a participant may withdraw from the study for any reason at any time.

Removal by Qualified Investigator:

Participant discontinuation should be considered at the discretion of the qualified investigator. The circumstances of any discontinuation must be documented in detail in the participant file and final report. If possible, the evaluations planned for the end of treatment will be carried out at the time when the participant is withdrawn from the study. A participant leaving the study prematurely will NOT be replaced by another. It is understood by all concerned that an excessive rate of withdrawals can render the study un-interpretable, thus unnecessary withdrawal of participants should be avoided.

Criteria for removal of participants from the study includes:

Clinical reasons

A participant may be withdrawn from the study if, in the opinion of the qualified investigator, it is not in the participant's best interest to continue. Any participant who experiences a serious adverse event (SAE) may be withdrawn from the trial at the discretion of the qualified investigator. A participant will also be

Protocol 19RNHB: A randomized, double-blind, comparator-controlled, cross-over study to investigate the safety and efficacy of RiaGev[™] in healthy adults

withdrawn due to adverse events causing clinically significant illness or the need for prohibited medication(s) during the trial. Any female participant who becomes pregnant during the course of the trial will be withdrawn.

Protocol violation

Any participant found to have entered this study in violation of the protocol will be discontinued from the study at the discretion of the qualified investigator. This will include any participant found to have been inappropriately enrolled (did not meet eligibility criteria). Participant non-compliance includes failure to show up for study visits, failure to take the investigational product as directed, or refusal to undergo study visit procedures. Participants who are found to be taking prohibited medications or supplements without the knowledge of the qualified investigator will also be withdrawn. Any major protocol deviations (i.e. those that increase the risk to participants and/or compromise the integrity of the study or its results) will result in participant discontinuation.

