8.5 Directions

Participants will be instructed to take two doses of the IP daily, once in the morning and once in the evening. Each dose will be 3 capsules, one dose will be administered immediately before breakfast and the other dose will be administered immediately before dinner. In both study periods, on day 1 only the evening dose will be administered and on day 8 only morning dose will be administered. The Clinic staff will instruct participants to save all unused and open packages and return them to Prism Clinical for a

determination of compliance. If a dose is missed participants are instructed to consume the missed dose anytime on the same day, except at bedtime. Participants will be advised not to exceed two servings daily.

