9.4 Visit 3 - (period 1- Day 3+1 Day)

Participants will return to the clinic one hour after consuming investigational product/placebo for Visit 3 assessments with unused investigational product, completed Subject sleep and treatment diary, saliva kit and food records.

Visit 3 assessments include:

- 1. Review concomitant therapies
- 2. Seated resting blood pressure and heart rate measurements
- 3. Weight measurements (BMI calculation)
- 4. Return unused investigational product in the original packaging and remnants and calculate compliance by counting the returned unused investigational product
- 5. Return saliva collection kit
- 6. Review AEs
- 7. Collect food record and subject sleep and treatment diary for review
- 8. Collect blood sample for NAD+ analysis
- 9. Administer CIS questionnaire
- 10. Re-dispense 7-Day Food Record
- 11. Dispense Subject sleep and treatment Diary
- 12. Dispense new saliva collection kit
- 13. Dispense new investigational product and instruct participants on use

The next visit will be scheduled for visit 4 (period 1- Day 5)

Reminders for participants prior to their next in-clinic visit:

- 1. Abide by instructions for medications as per Section 7.3.1 and OTC medications, supplements, and food/drinks as per Section 7.3.2
- 2. Maintain current level of physical activity and sleep schedule
- 3. Complete and return the food record and sleep and treatment diary
- 4. Participants will be advised to follow the dietary guideline (see Appendix 15.3)
- 5. Collect saliva in the morning 15 minutes after waking and prior to consumption of food
- 6. Return to clinic one hour after consuming investigational product/placebo and breakfast on the next visit day

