10.2.2 Treatment and Follow-up of Laboratory Abnormalities

In the event of participant-initiated withdrawal or clinically significant unexplained abnormal laboratory test values, the participant will be withdrawn from the treatment and will remain in the study and be required to attend all remaining study visits as part of a safety arm.

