11 STATISTICAL EVALUATION

11.1 Determination of Sample Size

The planned total sample size will be 18 with 9 participants randomized to each treatment schedule. This sample size will enable detection of a difference of 8.7 pMol/mg protein in NAD+ concentration between the two treatments at an overall 5% significance level and 80% power. This sample size takes into account a loss to follow up rate of 20%.

This calculation is based on a critical difference in NAD+ concentration, between NR and placebo of 6.1 pMol/mg protein and a standard deviation of 11.04 units reported in a study by Martens et al. (2018)(13).

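### Two consecutive non-compliant visits mean removal from the whole study, so four missed early doses can cost the Day 8 NAD+ value and all of Period 2; the expected loss is small and cheap to avoid

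*Protocol*

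**What the plan says.** Protocol section 9.13 calculates compliance from returned product at each visit. Participants below 80% or above 120% are counselled. Those below 70% or above 130% are non-compliant, and "any participant demonstrating non-compliance for two consecutive visits will be withdrawn from the study".

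Section 8.5 sets two doses a day, except that "on day 1 only the evening dose will be administered and on day 8 only morning dose will be administered". It also allows same-day make-up: "If a dose is missed participants are instructed to consume the missed dose anytime on the same day, except at bedtime". The reminders in section 9.4 for the following visit read: "Return to clinic one hour after consuming investigational product/placebo and breakfast on the next visit day". The morning dose on that visit day therefore falls before the count; section 9.4 sets Visit 3 itself one hour after dosing too.

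Section 7.4 states: "A participant leaving the study prematurely will NOT be replaced by another". It gives the qualified investigator general discretion over discontinuation, but says that major deviations "will result in participant discontinuation". It also asks for the end-of-treatment evaluations to be done at withdrawal where possible.

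Section 10.2.2 treats two other situations differently: withdrawal on the participant's own initiative, and unexplained laboratory results of clinical significance. In those cases it says that the person "will be withdrawn from the treatment and will remain in the study and be required to attend all remaining study visits". It labels this continued attendance a safety arm. Non-compliance is not listed there.

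On sample size, section 11.1 says: "This sample size takes into account a loss to follow up rate of 20" per cent. Section 11.2 and SAP 1.9 require at least 80% of doses for the PP set. SAP 2.4.1 allows last-observation-carried-forward or multiple imputation in the ITT analysis.

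**The concern.** The primary endpoint is the change in NAD+ from baseline to Day 8 in each period of a two-period crossover with 18 people. A participant removed on Day 5 of Period 1 has no observed Day 8 value on the first product and nothing at all on the second, so there is no within-person contrast. The Day 3 and Day 5 values stay in the SAP mixed model, but the Day 8 value has to be imputed although its visit was already scheduled.

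The removal also depends on behaviour after randomization. If doses are skipped for a reason connected with the product, the missing data could be informative. That is an inference, since the documents give no reasons for missed doses.

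The rule is not needed to keep poor compliers out of the PP analysis, which has its own compliance and major-violation criteria.

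**Working it through.** **1. The plan's own sample size.** Inputs from section 11.1: difference 8.7, SD 11.04, 5% significance, 80% power, 20% loss. I assume a two-sided test and treat 11.04 as the SD of the within-person difference; the protocol states neither. A paired t-test then needs 15 completers (power 81.0%), and 15 × 1.2 = 18, the planned number. (15 / 0.8 = 18.75 would give 19.) The planned loss is 0.20 × 18 = 3.6 people.

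**2. Doses expected per visit (section 8.5, nominal days).**
- Visit 2 to Visit 3: Day 1 evening, Day 2 twice, Day 3 morning = 4
- Visit 3 to Visit 4: Day 3 evening, Day 4 twice, Day 5 morning = 4
- Visit 4 to Visit 5: 5 at home + 1 in clinic = 6
- Period total: 4 + 4 + 6 = 14

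**3. When the rule applies.** Missing 1 of 4 gives 3/4 = 75%, which leads to counselling only. Missing 2 of 4 in both intervals gives 2/4 = 50% and 2/4 = 50% per interval, or 2/4 = 50% and 4/8 = 50% cumulatively. Withdrawal falls at Visit 4 (Day 5) either way. If the +1 day windows are used, an interval holds 6, 4 or 2 doses, and two misses give 66.7%, 50% or 0%, all below 70%.

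The same person could still finish the period at 10/14 = 71.4%, above the 70% line. If the second failure comes at Visit 5 instead, the Day 8 sample can still be taken and only Period 2 is lost.

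**4. How often.** The documents give no miss rate. I assume 10% and 20%, independent misses, and no effect of counselling or make-up doses. X and Y are the doses missed in the first and second interval.
- Per interval: P(X ≥ 2)². With 4 doses at risk, P(X ≥ 2) is 5.23% / 18.08%.
- Cumulative: X ≥ 2 and X + Y ≥ 3 (5/8 = 62.5% fails, 6/8 = 75% passes), that is P(X = 2) × P(Y ≥ 1) + P(X ≥ 3). At 10%: 0.0486 × 0.3439 + 0.0037 = 0.0204. At 20%: 0.1536 × 0.5904 + 0.0272 = 0.1179.

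Probability of Day 5 removal in Period 1, with expected number of 18 in brackets:

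| Counting | 10% missed | 20% missed |
|---|---|---|
| Per interval, all 4 doses at risk | 0.27% (0.05) | 3.27% (0.59) |
| Cumulative, all 4 at risk | 2.04% (0.37) | 11.79% (2.12) |
| Per interval, visit-morning dose always taken | 0.08% (0.01) | 1.08% (0.19) |
| Cumulative, visit-morning dose always taken | 0.83% (0.15) | 5.48% (0.99) |

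**5. Power.** Paired t-test, two-sided 5%, difference 8.7:

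| Assumed SD of difference | n = 18 | 17 | 16 | 15 |
|---|---|---|---|---|
| 9 | 97.1% | 96.2% | 95.0% | 93.5% |
| 11.04 | 88.3% | 86.2% | 83.8% | 81.0% |
| 13 | 76.3% | 73.6% | 70.6% | 67.4% |

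Each loss costs about 1 to 3 points. This calculation gives a removed person no weight, whereas the SAP mixed model keeps the Day 3 and Day 5 values, so the cost is likely an upper limit.

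**The case against.** Stopping people who twice take less than 70% of their doses is a defensible choice in a short healthy-volunteer study. The rule is pre-specified and identical for both products, and the ITT analysis has planned imputation. Counselling starts below 80%, and make-up doses reduce the chance of a second failure. Product is returned and newly dispensed at Visits 3 and 4, so per-interval counting is the more natural reading, and it gives the smaller figures. The investigator also has general discretion under section 7.4. Most of this stands, and it is why the point is minor. The discretion argument is weaker, because section 9.13 is specific to this trigger and leaves no room for judgement.

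A reader might go further and infer two things that the documents do not support.

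- **That nothing more is collected after Day 5.** Section 7.4 provides for end-of-treatment evaluations at withdrawal where possible, Visit 4 already takes an NAD+ sample, and section 10.2.1 follows adverse events until they resolve or stabilise. What cannot be recovered is the Day 8 value and Period 2.
- **That section 10.2.2 already supplies the remedy.** It is only a partial precedent. It sits under laboratory abnormalities, describes off-product follow-up in a safety arm, and provides clearly neither for efficacy sampling for ITT nor for dosing with the second product.

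**Conclusion.** The point holds as a minor design weakness. Section 9.13 mandates study withdrawal, and four missed doses among the first eight can trigger it on Day 5, losing the Day 8 NAD+ value and Period 2 without replacement. That conclusion rests only on the text and the dose schedule, and it holds under either way of counting and within the visit windows.

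The size rests on assumed miss rates of 10% to 20% with independent misses: roughly 0.05 to 0.6 of 18 removed per interval, or 0.4 to 2.1 cumulatively, before counselling and make-up doses. All are below the planned 3.6.

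It would be tempting to conclude that the rule endangers the trial's power. At an SD of the difference of 11.04, one or two removals alone leave power at 86.2% or 83.8%. At an SD of 13 it is below 80% even with all 18, so the shortfall there is not due to this rule. Such removals do, however, use up the same 20% allowance as unavoidable dropout.

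**What to change.** Amend section 9.13, and align section 7.4, along these lines:

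- Non-compliance at two consecutive visits is recorded as a protocol deviation and leads to counselling and exclusion from the PP set, not to withdrawal from the study. The PP exclusion should be stated outright, because the 80% criterion does not say whether it applies per period or overall. Four misses in one period and none in the other would be 24/28 = 85.7% overall.
- If the participant agrees, all scheduled visits and all efficacy and safety samples continue for ITT, including Day 8 NAD+.
- The participant crosses over to the Period 2 product as randomized, unless the qualified investigator stops product for safety.

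The cost is protocol wording, since the visits and samples are already planned. The downside is slight dilution of the ITT estimate by poor compliers, with the PP analysis as the contrast. The change is useful only if conduct is still open; SAP 1.8 reports that 18 participants had been enrolled, so it may come too late.
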